9.3.3.2. Covariates

All members of the study cohorts will be classified according to covariates identified in the claims data. Note that only baseline (ie, pre-treatment) covariates will be considered for inclusion in the propensity score models. Covariates assessed during pregnancy, which may occur after treatment initiation or infection, will be described and/or used for subgroup analysis. Recognizing that a narrower (for time-varying covariates, etc.) or broader (for chronic conditions, etc.) window of assessment may better capture select patient attributes of

interest, specific covariates may be assessed using alternate time period(s), which are noted below.

In addition to the covariates listed below, Optum will identify baseline predictors on an empiric basis by examining the most frequently occurring diagnoses, drugs dispensed, and procedures performed among pregnancies with and without PAXLOVID exposure. These empiric covariates will be considered for inclusion in the propensity score models used for IPTW.

Detailed definitions and code lists for covariates will be included in the SAP.

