9.7.2.1. Propensity score modeling

For the final analysis, each pregnancy will be assigned a propensity score, a measure of the probability of receiving PAXLOVID versus a comparator treatment (or no treatment), given the patient's baseline characteristics. This propensity score will be utilized to implement IPTW to adjust for confounding.

IPTW produces groups (after weighting) that have similar patterns of the presence or absence of a large number of factors. The key to propensity score estimation is to perform a rich statistical analysis of the predictors of PAXLOVID exposure. The propensity score logistic regression model can incorporate demographic, comorbidity, treatment history, predictors of treatment choice, and co-medication indicators, as well as other potential confounders and risk factors.

In this study, all of the propensity score model variables will be determined from claims data and will be determined without respect to outcome status. For a given covariate pattern, the propensity score is the fitted value of the probability of being a member of the PAXLOVID group, given membership in the study population and the covariate pattern. To the extent that the decision to be dispensed PAXLOVID depends on the health characteristics of the patient at the time of the decision, the propensity score models the clinical decision-making process.

Four sets of propensity scores will be created: 1 for each of the comparator cohorts (Cohorts 2 and 3) versus Cohort 1, and 1 for each of the exposure windows (first trimester, full pregnancy). The decision to include variables in the model will be based on *a priori* knowledge (eg, expected confounder or known risk factor of adverse pregnancy/infant outcomes).

The covariates listed in Section 9.3.3.2.1 will be considered for inclusion in the model as independent (predictor) variables. The propensity score model will only include covariate information during the baseline period (prior to and including the index date). Hence, the propensity scores will incorporate characteristics at the start of the pregnancy. In addition to the pre-specified variables in Section 9.3.3.2.1, the most common diagnoses, procedures, and medications observed prior to estimated date of conception will be evaluated to ensure no important confounders are missed.

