If there are too many variables given the number of pregnancies exposed to PAXLOVID (eg, < 10 exposed pregnancies for every variable in the propensity score model), the number of variables may be reduced using a LASSO model. Variables with an estimate of 0 in the LASSO model will be dropped from the propensity score variable list and a logistic regression model will be run using the remaining variables. For variable pairs that are highly correlated (eg, correlation coefficient > 0.9), 1 may be eliminated.

As patterns of prescribing tend to change over time, particularly for newly available products, with early adopters of the formulation (both physician and patient) tending to differ from late adopters, prediction equations need to account for these secular changes. As such, the propensity score models will incorporate calendar time to take into account the changing nature of the patient pool and COVID treatment guidelines over time. Incorporating calendar time may also account for changes in COVID-19 variants and severity over time (eg, Delta versus Omicron).

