Covariance between observations will be taken into account via robust standard errors if multiple pregnancies per woman are observed (Mansournia et al. 2021). Known confounders that are strongly associated with PAXLOVID use and the pregnancy or infant outcomes, or that remain imbalanced after weighting via IPTW, will also be included in the outcome regression models if standardized mean differences exceed >0.2 after IPTW (Austin 2009). Baseline covariates with an imbalance of 0.1-0.2 will be considered individually, taking into account their prevalence. Prior history of COVID-19 and the use of COVID-19 therapies during baseline and after cohort entry may be used for subgroup analysis. Other pregnancy characteristics (characteristics that are identified after baseline and that are therefore not incorporated into the propensity score models), such as COVID-19 severity, may also be considered for subgroups in secondary analysis.

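### The optional LASSO step can delete pre-specified outcome risk factors from the propensity score; they should be held in the model

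*Protocol*

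**What the plan says.** All references are to the protocol.

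- **Basis for inclusion (9.7.2.1).** Variables are chosen on a priori knowledge, for example "expected confounder or known risk factor of adverse pregnancy/infant outcomes". Model variables "will be determined without respect to outcome status". There are four models: two comparator cohorts by two exposure windows.
- **Extra candidates (9.3.3.2).** Frequent diagnoses, drugs and procedures are added empirically: "These empiric covariates will be considered for inclusion in the propensity score models used for IPTW".
- **Trigger and rule (9.7.2.1).** If there are too many variables for the number exposed ("eg, < 10 exposed pregnancies for every variable in the propensity score model"), "the number of variables may be reduced using a LASSO model". Then "Variables with an estimate of 0 in the LASSO model will be dropped from the propensity score variable list", and a logistic model is fitted to what remains.
- **Calendar time (9.7.2.1, next paragraph).** "the propensity score models will incorporate calendar time".
- **Balance checks.** Under 9.7.2.1.1, a weighted standardized difference above 0.1 may be treated as imbalance, and the variable may go into the outcome model. Under 9.7.2.3, imbalanced confounders "will also be included in the outcome regression models if standardized mean differences exceed >0.2 after IPTW", and differences of 0.1 to 0.2 are judged one by one.
- **Origin.** The amendment table in Section 5 records the LASSO step as a regulatory request.

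**The concern.** A covariate confounds through the product of its link with treatment and its link with outcome. A LASSO fitted to treatment sees only the first link. It can set to zero a factor that is modestly related to PAXLOVID use, however strongly that factor drives preterm birth, SGA, spontaneous abortion or MCM. It will tend to keep a variable that predicts PAXLOVID use and nothing else, which costs precision and removes no confounding.

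The section therefore states one principle, prior knowledge of outcome risk, and then fixes a rule that can override it without exempting the variables the principle was meant to secure. One lost factor matters little. Several lost together, acting in the same direction, leave confounding in the weighted prevalence ratio, possibly with each variable below the level at which outcome-model adjustment is committed.

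**Working it through.** **1. What the LASSO models.** The dependent variable is not named. Selection ignores outcome status and the trigger counts exposed pregnancies, so treatment is the natural reading.

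**2. When the step arises.** At 10 exposed per variable (exposed / 10), using Section 9.5 sizes:

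- 938 (MCM, RR 2.0, 1:2): 93 variables
- 482 (MCM, RR 2.5, 1:2): 48 variables
- 3,352 (MCM, 5:1 against Cohort 2): 335 variables

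At 5:1, 938 exposed implies 938 / 5 ≈ 188 in Cohort 2.

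**3. One omitted binary risk factor.** Bias factor = [p1(RR−1)+1] / [p0(RR−1)+1], with p0 = 10% (assumed).

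- SMD 0.1 (p1 ≈ 13.2%): RR 2 gives 1.132/1.100 = 1.029; RR 3 gives 1.264/1.200 = 1.053.
- SMD 0.2 (p1 ≈ 16.8%): RR 2 gives 1.168/1.100 = 1.062; RR 3 gives 1.336/1.200 = 1.113.

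**4. Several together.** With an exposure odds ratio of 1.2, 10% becomes 11.8%, an SMD of about 0.06 and a factor of about 1.016. Twelve such factors in the same direction give 1.016^12 ≈ 1.21 before weighting.

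**5. Simulation A, no outcome-model adjustment.** Assumed: 12 risk factors (10% prevalence, exposure OR 1.2, outcome RR 2), 10 treatment-only predictors (OR 1.8) and 80 noise variables, 102 in all. Method: 5-fold cross-validated L1 logistic model of treatment, logistic refit, ATT weights e/(1−e). Bias is the log ratio of mean outcome risk, treated against weighted comparators. One set used 25 runs per setting; a second set under the same assumptions was run separately.

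- 938 v 188: 22% of risk factors kept in both sets, against 68% of treatment-only predictors (first set). Bias was 0.106 and 0.15 unforced, against 0.018 and 0.06 with risk factors forced in. The gain from forcing is 0.088 and 0.09, so the gain is steadier than the level.
- 3,352 v 670, or 938 v 4,690 (five sampled comparators each), cross-validation-minimum penalty: 61-67% kept, bias about 0.01-0.02.
- The same sizes, sparser penalty: 6-13% kept (first set), bias 0.14-0.17 and 0.10-0.15 in the two sets. On the ratio scale e^0.10 = 1.11 and e^0.17 = 1.19.

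**6. Simulation B, with the balance backstop.** Assumed: 8 risk factors (SMD 0.12 in the rows below, RR 1.35 per SD), 8 treatment-only predictors (SMD 0.5), the rest noise; true ratio 1.0. Cells show the ratio unforced / forced.

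| Exposed v comparators (variables) | Penalty | No adjustment | Adjust >0.2 | Adjust >0.1 |
|---|---|---|---|---|
| 482 v 964 (60) | CV minimum | 1.029 / 1.017 | 1.042 / 1.036 | 1.039 / 1.037 |
| 482 v 964 (60) | 1-SE | 1.144 / 1.021 | 1.123 / 1.029 | 1.066 / 1.037 |
| 482 v 96 (60) | CV minimum | 1.137 / 1.085 | 1.141 / 1.135 | 1.080 / 1.069 |
| 482 v 96 (60) | 1-SE | 1.255 / 1.075 | 1.108 / 1.106 | 1.067 / 1.071 |
| 938 v 188 (100) | CV minimum | 1.057 / 1.011 | 1.142 / 1.135 | 1.102 / 1.097 |
| 938 v 188 (100) | 1-SE | 1.229 / 1.020 | 1.158 / 1.130 | 1.097 / 1.094 |

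Across this simulation the LASSO dropped 18-52% of risk factors (CV minimum) or 56-88% (1-SE) and kept 95-100% of treatment-only predictors. At 1:2, only 1-8% of dropped risk factors exceeded SMD 0.2; at 5:1, 26-45% did.

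**The case against.** The best case for leaving the text alone is substantial.

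- **The step may never run.** It is optional. At 3,352 exposed, 102 variables would leave about 33 exposed per variable, so the example trigger would not be met. At 938 it is just met (938/102 ≈ 9.2). This stands.
- **Calendar time.** A reader might infer from the drop rule that calendar time can be deleted. The next paragraph commits it to the models, so that reading fails. Only an explicit exemption is missing.
- **MCM against Cohort 2.** A reader might infer that the MCM comparison will be about 11% too high, from the 938 v 188 result. Section 9.5 requires 3,352 and 670 for MCM at 5:1, where bias was about 1-2% under a CV-minimum penalty. That inference fails. The smaller size could still arise for spontaneous abortion, SGA or preterm birth, whose exposed minimums are 127, 251 and 251.
- **The backstop.** It is more than the 0.2 rule, and it narrows the gap. With everything above 0.1 adjusted, forcing gains at most about 3 points in the table and once nothing. At 5:1 it gains little after the 0.2 rule as well. But adjustment above 0.1 is discretionary. At 1:2 with the sparser penalty, the committed rule alone leaves 1.123 against 1.029. At 938 v 188 (CV minimum), adjusting above 0.2 moved the forced estimate from 1.011 to 1.135, so it is no dependable substitute. Section 9.9 itself says outcome regression can carry few confounders here.
- **Stacked inputs.** Bias in one direction is an assumption of the simulations, not a consequence of the text. This stands.
- **Left to the SAP.** The penalty may be set there. The drop rule is fixed in the protocol.
- **Regulatory request; exposure predictors.** Section 9.7.2.1 also calls for rich modelling of what predicts PAXLOVID use. Neither point requires that known outcome risk factors be removable.

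**Conclusion.** The point holds as a weakness in method. The protocol fixes a rule that can remove the variables it says are chosen on prior knowledge, and protects only calendar time. It does not show that any planned estimate will be biased.

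Under the assumed inputs, and before outcome-model adjustment, residual bias is about 1-2% where comparators are ample, or at 3,352 v 670, with a CV-minimum penalty. It is about 10-20% with a sparser penalty or a small Cohort 2. Size depends on the unseen penalty, on risk factors acting in the same direction, and on how far the discretionary balance adjustments are used. The simulations carry no stated Monte Carlo error; at 938 v 188 the two sets gave 0.106 and 0.15. The change is worth making because it is cheap and restores the principle the section already states.

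**What to change.** Amend the LASSO paragraph of Section 9.7.2.1 to say that:

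1. the a priori confounders and known outcome risk factors from Section 9.3.3.2.1, with calendar time and gestational timing of the index date, enter every propensity model unpenalised;
2. LASSO selects only among the empirically identified covariates and those listed items that are not outcome risk factors;
3. weighted balance is reported for all pre-specified covariates, including any dropped.

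This keeps the LASSO step. The cost is a sentence or two and a penalty-factor setting, plus about 2-3 points of effective sample size in the example (50% against 47% in the first set at 938 v 188). The loss would be larger if many variables were forced into a small Cohort 2 model. With 188 comparators, ten per variable would allow only about 18, so the forced list should be limited to genuine outcome risk factors.

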9.7.2.1.1. Inverse probability of treatment weighting

Propensity scores will be used to calculate IPTW weights and to weight each pregnancy in the exposure cohorts. For the IPTW analysis, a sample of comparators may be selected if a large number of pregnancies is accrued into the comparator cohorts (particularly the Untreated Comparator cohorts). This would be done to improve study efficiency through reducing the number of potential medical records to be sought among the comparator cohorts. If implemented for the final analysis, up to 5 comparators per PAXLOVID-exposed pregnancy will be sampled. Sampling of comparators will be performed via random sampling, without replacement, within strata of maternal age and calendar time based on the distributions within the PAXLOVID cohort. Sampling in this manner ensures that comparator pregnancies are approximately matched, at ECD, on the important covariates of maternal age and calendar time.

The IPTW weights will be defined such that the causal estimate is the average treatment effect among the treated (ATT) (Austin & Stuart 2015). Briefly, to estimate the ATT, the weights (w_{ATT}) are defined such that every PAXLOVID-exposed pregnancy receives a weight of 1, while the comparator pregnancies receive weights that are a function of the propensity score:

$$w_{ATT} = Z + \frac{\mathrm{e}(1-\mathrm{Z})}{1-\mathrm{e}},$$

where Z is the indicator for PAXLOVID exposure, e is the propensity score, and X is the covariate pattern used to predict PAXLOVID exposure (Section 9.7.2.1):

$$e = \Pr(Z = 1 | X).$$

Balance of covariates among the weighted cohorts will be assessed using the weighted standardized difference ($SD_{weighted}$) comparing the weighted study cohorts. Any variables with an absolute $SD_{weighted} > 0.1$ may be considered imbalanced. If specific variables remain imbalanced after IPTW, they may be included as independent predictors in outcome models. Trimming of extreme weights will be considered (Stürmer et al. 2014).

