9.3. Variables

9.3.1. Outcomes

The primary outcome is MCM. The secondary outcomes are SA, induced termination, stillbirth, livebirth, SGA, preterm birth, postnatal growth deficiency and

infant developmental. The study outcomes will be identified by ICD-10 diagnosis and procedure codes, CPT^{®2} procedure codes, and HCPCS procedure codes on claims. All outcomes will initially be identified via claims-based algorithms. Potential cases of MCM, induced termination, SGA, preterm birth, postnatal growth deficiency and infant developmental delay, and a sample of livebirths identified via claims-based algorithms will be adjudicated via medical records.

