9.3.1.3. Medical record confirmation of outcomes

Pregnancy and infant outcomes will be assessed using claims-based algorithms from the literature with adequate PPVs when available, otherwise confirmed via medical records. Andrade et al. observed a PPV of 83% for their ICD-10-based stillbirth algorithm, developed within an electronic health record database (Andrade et al. 2021). A recent Optum publication observed a PPV of 84.7% for the identification of SA (Chomistek et al. 2022). Optum proposes to use these published algorithms to identify SA and stillbirth.

Given that most pregnancies are expected to end in a livebirth, a random sample of 200 livebirths will be selected for medical record confirmation and validation of the livebirth identification algorithm, which relies on the presence of outcome-related ICD-10 codes. This conservative sample size is sufficient to exclude from the 95% confidence interval (CI) a PPV <80% if the true PPV is 85% (Schaeffer et al. 1990). Livebirths are identified via ICD-10 codes shown in ANNEX 2. ADDITIONAL INFORMATION.

Using medical records to confirm pregnancy and infant outcomes allows for a highly sensitive and specific outcome definition because medical records may be sought for all potential outcomes (high sensitivity) and each potential outcome is adjudicated (high specificity). The literature will be re-assessed following delivery of the final accrual report to identify alternative stillbirth and/or SA algorithms and algorithms for the remaining outcomes. If suitable algorithms are found, the proposed approach may be modified to use algorithms for additional outcomes (Tonelli et al. 2016).

For outcomes for which medical record confirmation is deemed necessary, a detailed review of the chronological listing of relevant claims (ie, claims profile) will be reviewed for each of the potential cases in order to:

- Determine if the claims listing for each potential case contains sufficient information to be included in the medical record procurement process; and
- Determine the medical site of treatment most likely to yield medical records with the necessary information to confirm case status.

Optum, with input from a clinician, will develop a medical record review form that will include clinical elements necessary to confirm the outcome diagnosis. Providers will be asked to send all available medical information occurring during the period of interest

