9.5. Study size

The planned sample size incorporates several assumptions derived from published literature, including the following approximate prevalence of pregnancy outcomes:

- Under 1% of pregnancies result in stillbirth (FDA 2002)
- 14% of pregnancies result in SA or miscarriage (FDA 2002)
- 18% of pregnancies have historically been expected to end in induced termination (Jones et al. 2017)
- 3% of live born infants have a major birth defect in the US each year (March of Dimes 2015)
- 10% of live born infants are born preterm or SGA (CDC 2008, Ferré et al. 2016)

Based on these reference percentages, the following assumptions were made for sample size calculation:

- $\alpha = 0.05$
- Power=0.8
- 1:2 matching
- Outcome prevalence as cited above

Table 1 and Table 2 show the minimum required number of PAXLOVID-exposed pregnancies required to proceed to the secondary objective of comparative analyses. Comparative analyses will be conducted if the sample size to detect a RR > 2.0 is achieved for each outcome; target sample size may be achieved for some outcomes but not others.

To detect a RR > 2.0 at 80% power a minimum of 127 PAXLOVID-exposed pregnancies are required for SA, 251 for SGA and preterm birth, and 2,212 for stillbirth, the rarest of the outcomes (Table 1). A minimum of 938 PAXLOVID-exposed pregnancies during the first trimester are required for the primary outcome of MCM (Table 2).

Fewer PAXLOVID-exposed pregnancies are required to detect an RR of > 2.5 at 80% power: 63 for SA, 127 for SGA and preterm birth, and 1,142 for stillbirth. For MCM, the minimum number of pregnancies with PAXLOVID exposure during the first trimester is 482. These estimates are based on 1:2 matching; however, the analyses for this study will utilize IPTW for confounding adjustment. Sample size calculations are based on 1:2 matching as a conservative estimate due to the retention of all eligible pregnancies in IPTW. Power for the analysis of induced termination will be similar to that for SA. The majority of pregnancies end in livebirth; therefore, power is expected to be adequate for this outcome.

Table 1. Sample Size Required for 80% Power to Detect Relative Risks (As or More Extreme) for Pregnancy Outcomes, with 1:2 Matching

Outcome	Prevalence of Outcome	RR	PAXLOVID-Exposed Pregnancies with Observed Outcomes Needed*	PAXLOVID-Exposed Pregnancies Needed**
SA	14%	2	101	127
		2.5	50	63
Stillbirth	1%	2	1,769	2,212
		2.5	913	1,142

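### Comparator sampling to 5:1, meant only to save medical records, also removes Cohort 3 pregnancies from analyses that need no case-by-case records

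*Protocol*

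**What the plan says.** Protocol Section 9.7.2.1.1 makes the step optional: "For the IPTW analysis, a sample of comparators may be selected if a large number of pregnancies is accrued into the comparator cohorts". If it is used, "up to 5 comparators per PAXLOVID-exposed pregnancy will be sampled", at random and without replacement, within strata of maternal age and calendar time. The stated purpose is "This would be done to improve study efficiency through reducing the number of potential medical records to be sought among the comparator cohorts". The section sets no limit by outcome.

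Other sections decide which outcomes need records:
- Section 9.3.1 sends these to adjudication: "Potential cases of MCM, induced termination, SGA, preterm birth, postnatal growth deficiency and infant developmental delay, and a sample of livebirths". Spontaneous abortion and stillbirth are not on the list.
- Section 9.3.1.3, on those two: "Optum proposes to use these published algorithms to identify SA and stillbirth". On livebirth: "a random sample of 200 livebirths will be selected for medical record confirmation". The same section caps record requests at 550.
- Section 9.7.2.3 commits to presenting claims-identified analyses. It also admits outcomes from validated published algorithms to the primary comparative analyses.

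Section 9.5 justifies the study size as follows: "Sample size calculations are based on 1:2 matching as a conservative estimate due to the retention of all eligible pregnancies in IPTW".

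**The concern.** The rule acts on pregnancies, while its purpose concerns records. Dropping a Cohort 3 pregnancy saves a request only if that pregnancy would have been a potential case of an adjudicated outcome. For spontaneous abortion, stillbirth, livebirth and every claims-identified analysis, it removes comparator data and spares no record.

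Cohort 3 is the plan's abundant comparator; Section 9.5 reports that Cohort 2 is accruing at about one pregnancy per five PAXLOVID pregnancies. At stake is some precision in the Cohort 1 versus Cohort 3 contrast, most of all for stillbirth, where Section 9.5 already doubts the power. The sampling option and the retention statement in Section 9.5 also cannot both describe the same analysis.

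**Working it through.** **1. The plan's own figure.** Table 1 asks for 1,769 PAXLOVID pregnancies with observed outcome for stillbirth (1% unexposed, RR 2, two-sided 5%, likelihood-ratio chi-square, 1:2). Dividing by 0.80 gives the stated 2,212. Using noncentral chi-square power for that test:
- As labelled (one exposed at 2% to two unexposed at 1%), 80% power needs 1,643.
- 1,769 is reproduced exactly only with the allocation reversed (one unexposed to two exposed).
- At the labelled 1:2, 1,769 gives 83% power, so the stated size is slightly generous.

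I use 1,769 below because Section 9.5 makes the tabulated size the trigger for a comparative analysis.

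**2. Comparators available per PAXLOVID pregnancy.** The counts are from Table 3, before eligibility criteria, and assume no overlap among the treated subsets.
- 2021 to mid-2022: 19,581 + 5,385 − 564 − 409 − 206 − 11 = 23,776; 23,776 / 1,021 = 23.3.
- Partial 2022 alone: 5,385 − 379 − 225 − 11 = 4,770; 4,770 / 726 = 6.6.

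The pooled figure includes 2021, nearly all of it before the authorisation of 22 December 2021. The 2022 figure is incomplete. The final ratio R is therefore an assumption; I take 6.6 to 25. A cap of 5 then drops 1 − 5/6.6 = 24% to 1 − 5/25 = 80% of Cohort 3.

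**3. Precision near the null.** Take the variance of the log prevalence ratio as proportional to 1/n1 + D/n0, where D is the design effect of the comparator weights. The variance at 5:1 relative to full retention is (1 + D/5) / (1 + D/R).

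| R | D | Variance ratio | Information lost | Interval wider by |
|---|---|---|---|---|
| 6.6 | 1 | 1.2000/1.1515 = 1.042 | 4% | 2% |
| 10 | 1 | 1.2000/1.1000 = 1.091 | 8% | 4% |
| 25 | 1 | 1.2000/1.0400 = 1.154 | 13% | 7% |
| 6.6 | 2 | 1.4000/1.3030 = 1.074 | 7% | 4% |
| 25 | 2 | 1.4000/1.0800 = 1.296 | 23% | 14% |

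Information lost is 1 − 1/ratio; widening is √ratio − 1. D = 1 means equal weights. D = 2, held the same in sample and full cohort, is an illustration, because the protocol gives no value.

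**4. Power at the protocol's thresholds**, equal weights, RR 2, same test:

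| Outcome | Exposed with outcome observed | 5:1 | 6.6:1 | 20:1 |
|---|---|---|---|---|
| Stillbirth (1% v 2%) | 1,769 | 91% | 93% | 95% |
| Spontaneous abortion (14% v 28%) | 101 | 91% | 92% | 94% |

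**5. Where sampling does save records.** Nine outcomes are listed. Six go to adjudication: MCM, induced termination, SGA, preterm birth, postnatal growth deficiency and developmental delay. For those six, fewer comparator pregnancies mean fewer potential cases to request.

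**The case against.** The step is doubly conditional, and the SAP could limit it by outcome. For six of nine outcomes, including the primary one, it does what it is meant to do. Claims-identified analyses are not primary where an outcome needs record confirmation. A 5:1 sample keeps every PAXLOVID pregnancy and 2.5 times the comparators that Section 9.5 assumed. All of this stands, and it limits the size of the point. It does not supply a benefit for the analyses that need no records, and the protocol text as written covers them.

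A reader might infer more than the documents support:
- **That the study size is undermined.** It is not. With equal weights 5:1 is still more favourable than 1:2; the conflict is between the two statements on retention.
- **That stillbirth power falls badly at smaller accrual, for example 1,500 PAXLOVID pregnancies.** Section 9.5 would not run the stillbirth comparison below 2,212.
- **That a fifth to a third of the information is lost.** Such figures need a high assumed design effect that is the same in the sample and the full cohort. Sampling to the PAXLOVID distribution of age and calendar time should drop mainly low-weight pregnancies, so the true loss may be smaller.
- **That the strata waste the sample because comparators are only** "approximately matched, at ECD, on the important covariates of maternal age and calendar time" **and not at the index date.** Nothing in the protocol quantifies this. Calendar time of the index date and its interval from ECD are listed covariates (Section 9.3.3.2.1), and a long lag cannot arise in the first-trimester window.

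**Conclusion.** The point holds as an efficiency and consistency matter, with no bias shown. For spontaneous abortion, stillbirth, livebirth and the claims-identified analyses, comparator sampling loses precision with no offsetting saving in records, and it contradicts the retention statement in Section 9.5. The cost is modest: about 4-13% of the information with equal weights, and about two to four points of stillbirth power at the protocol's threshold, comparing 5:1 with 6.6:1 and 20:1. These figures rest on an assumed available ratio guided by pre-eligibility counts, and on equal comparator weights. Variable weights would raise them, and stratified sampling that removes mainly low-weight pregnancies would lower them. This is a cheap improvement to consider, not a defect that threatens the study.

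**What to change.** In Section 9.7.2.1.1:
- State that any comparator sampling applies only to record-confirmed outcomes. Alternatively, sample only the list of potential cases sent for record request, with known sampling fractions, and weight adjudicated cases by the inverse of the fraction.
- State that every eligible Cohort 3 pregnancy is kept for spontaneous abortion, stillbirth, livebirth and all claims-identified analyses.
- Align the retention sentence in Section 9.5 with whichever option is chosen.

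The cost is protocol and SAP wording, with no additional records or data. The downside is small: under the first option the analysis set differs by outcome and must be labelled so; under the second, the record-confirmed analyses need a sampling weight and a matching variance. The effective sample sizes already planned for interim reports 2 to 4 (Section 9.7.1) would show how variable the comparator weights are before the choice is fixed.
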